#### **6.1.4.5.1 Survival Follow-up**

Once a subject experiences confirmed disease progression or starts a new anti-cancer therapy, the subject moves into the survival follow-up phase and should be contacted by telephone every 12 weeks to assess for survival status until death, withdrawal of consent, or the end of the study, whichever occurs first.

### **6.2 Assessing and Recording Adverse Events**

An adverse event is defined as any untoward medical occurrence in a patient or clinical investigation subject administered a pharmaceutical product and which does not necessarily have to have a causal relationship with this treatment. An adverse event can therefore be any unfavorable and unintended sign (including an abnormal laboratory finding, for example), symptom, or disease temporally associated with the use of a medicinal product or protocol-specified procedure, whether or not considered related to the medicinal product or protocol-specified procedure. Any worsening (i.e., any clinically significant adverse change in frequency and/or intensity) of a preexisting condition that is temporally associated with the use of the Merck's product, is also an adverse event.

Changes resulting from normal growth and development that do not vary significantly in frequency or severity from expected levels are not to be considered adverse events. Examples of this may include, but are not limited to, teething, typical crying in infants and children and onset of menses or menopause occurring at a physiologically appropriate time.

Merck product includes any pharmaceutical product, biological product, device, diagnostic agent or protocol-specified procedure, whether investigational (including placebo or active comparator medication) or marketed, manufactured by, licensed by, provided by or distributed by Merck for human use.

Adverse events may occur during the course of the use of Merck product in clinical trials or within the follow-up period specified by the protocol, or prescribed in clinical practice, from overdose (whether accidental or intentional), from abuse and from withdrawal.

Adverse events may also occur in screened subjects during any pre-allocation baseline period as a result of a protocol-specified intervention, including washout or discontinuation of usual therapy, diet, placebo treatment or a procedure.

Progression of the cancer under study is not considered an adverse event unless it is considered to be drug related by the investigator.

All adverse events will be recorded from the time the consent form is signed through 30 days following cessation of treatment and at each examination on the Adverse Event case report

forms/worksheets. The reporting timeframe for adverse events meeting any serious criteria is described in section 6.2.3.1.

### **6.2.1 Definition of an Overdose for This Protocol and Reporting of Overdose to the Sponsor and to Merck**

For purposes of this trial, an overdose of pembrolizumab will be defined as any dose of 1,000 mg or greater ( $\geq 5$  times the indicated dose). No specific information is available on the treatment of overdose of pembrolizumab. Appropriate supportive treatment should be provided if clinically indicated. In the event of overdose, the subject should be observed closely for signs of toxicity. Appropriate supportive treatment should be provided if clinically indicated.

If an adverse event(s) is associated with (“results from”) the overdose of a Merck product, the adverse event(s) is reported as a serious adverse event, even if no other seriousness criteria are met.

If a dose of Merck’s product meeting the protocol definition of overdose is taken without any associated clinical symptoms or abnormal laboratory results, the overdose is reported as a non-serious Event of Clinical Interest (ECI), using the terminology “accidental or intentional overdose without adverse effect.”

All reports of overdose with and without an adverse event must be reported within 24 hours to the Sponsor and within 2 working days hours to Merck Global Safety. (Attn: Worldwide Product Safety; [contact])

### **6.2.2 Reporting of Pregnancy and Lactation to the Sponsor and to Merck**

Although pregnancy and lactation are not considered adverse events, it is the responsibility of investigators or their designees to report any pregnancy or lactation in a subject (spontaneously reported to them), including the pregnancy of a male subject's female partner that occurs during the trial or within 120 days of completing the trial completing the trial, or 30 days following cessation of treatment if the subject initiates new anticancer therapy, whichever is earlier. All subjects and female partners of male subjects who become pregnant must be followed to the completion/termination of the pregnancy. Pregnancy outcomes of spontaneous abortion, missed abortion, benign hydatidiform mole, blighted ovum, fetal death, intrauterine death, miscarriage and stillbirth must be reported as serious events (Important Medical Events). If the pregnancy continues to term, the outcome (health of infant) must also be reported.

Such events must be reported within 24 hours to the Sponsor and within 2 working days to Merck Global Safety. (Attn: Worldwide Product Safety; [contact])

### **6.2.3 Immediate Reporting of Adverse Events to the Sponsor**

#### **6.2.3.1 Serious Adverse Events**

A serious adverse event is any adverse event occurring at any dose or during any use of Merck's product that:

- Results in death;
- Is life threatening;
- Results in persistent or significant disability/incapacity;
- Results in or prolongs an existing inpatient hospitalization;
- Is a congenital anomaly/birth defect;
- Is a new cancer (that is not a condition of the study);
- Is associated with an overdose;
- Is another important medical event

Refer to Table 7 for additional details regarding each of the above criteria.

Any serious adverse event, or follow up to a serious adverse event, including death due to any cause other than progression of the cancer under study that occurs to any subject from the time the consent is signed through 90 days following cessation of treatment, or the initiation of new anti-cancer therapy, whichever is earlier, whether or not related to Merck product, must be reported within 24 hours to the Sponsor and within 2 working days to Merck Global Safety.

Non-serious Events of Clinical Interest will be forwarded to Merck Global Safety and will be handled in the same manner as SAEs.

Additionally, any serious adverse event, considered by an investigator who is a qualified physician to be related to Merck product that is brought to the attention of the investigator at any time outside of the time period specified in the previous paragraph also must be reported immediately to the Sponsor and to Merck.

**SAE reports and any other relevant safety information are to be reported to Georgetown DSMB, Hackensack eIRB, Merck Global Safety ([contact]).**

A copy of all 15 Day Reports and Annual Progress Reports is submitted as required by FDA, European Union (EU), Pharmaceutical and Medical Devices agency (PMDA) or other local regulators. Investigators will cross reference this submission according to local regulations to the Merck Investigational Compound Number (IND, CSA, etc.) at the time of submission. Additionally investigators will submit a copy of these reports to Merck & Co., Inc. (Attn: Worldwide Product Safety; [contact]) at the time of submission to FDA.

All subjects with serious adverse events must be followed up for outcome.

### 6.2.3.2 Events of Clinical Interest

Selected non-serious and serious adverse events are also known as Events of Clinical Interest (ECI) and must be recorded as such on the Adverse Event case report forms/worksheets and reported within 24 hours to the Sponsor and within 2 working days to Merck Global Safety. (Attn: Worldwide Product Safety; [contact])Events of clinical interest for this trial include:

1. an overdose of Merck product, as defined in Section 6.2.1 - Definition of an Overdose for This Protocol and Reporting of Overdose to the Sponsor, that is not associated with clinical symptoms or abnormal laboratory results.
2. an elevated AST or ALT lab value that is greater than or equal to 3X the upper limit of normal and an elevated total bilirubin lab value that is greater than or equal to 2X the upper limit of normal and, at the same time, an alkaline phosphatase lab value that is less than 2X the upper limit of normal, as determined by way of protocol-specified laboratory testing or unscheduled laboratory testing.\*

**\*Note:** These criteria are based upon available regulatory guidance documents. The purpose of the criteria is to specify a threshold of abnormal hepatic tests that may require an additional evaluation for an underlying etiology. The trial site guidance for assessment and follow up of these criteria can be found in the Investigator Trial File Binder (or equivalent). See Appendix 6 for ECI Reference Guidance.

#### 1. Additional adverse events:

A separate guidance document has been provided entitled “Event of Clinical Interest Guidance Document” (previously entitled, “Event of Clinical Interest and Immune-Related Adverse Event Guidance Document”).

ECIs (both non-serious and serious adverse events) identified in this guidance document from the date of first dose through 90 days following cessation of treatment, or 30 days after the initiation of a new anticancer therapy, whichever is earlier, need to be reported within 24 hours to the Sponsor and within 2 working days to Merck Global Safety. (Attn: Worldwide Product Safety; [contact]), regardless of attribution to study treatment, consistent with standard SAE reporting guidelines.

Subjects should be assessed for possible ECIs prior to each dose. Lab results should be evaluated and subjects should be asked for signs and symptoms suggestive of an immune-related event. Subjects who develop an ECI thought to be immune-related should have additional testing to rule out other etiologic causes. If lab results or symptoms indicate a possible immune-related ECI, then additional testing should be performed to rule out other etiologic causes. If no other cause is found, then it is assumed to be immune-related.

#### **6.2.4 Evaluating Adverse Events**

An investigator who is a qualified physician will evaluate all adverse events according to the NCI Common Terminology for Adverse Events (CTCAE), version 4.03. Any adverse event which changes CTCAE grade over the course of a given episode will have each change of grade recorded on the adverse event case report forms/worksheets.

All adverse events regardless of CTCAE grade must also be evaluated for seriousness.

Table 11 Evaluating Adverse Events

An investigator who is a qualified physician, will evaluate all adverse events as to:

V4.0 CTCAE Grading	Grade 1	Mild; asymptomatic or mild symptoms; clinical or diagnostic observations only; intervention not indicated.		
	Grade 2	Moderate; minimal, local or noninvasive intervention indicated; limiting age-appropriate instrumental ADL.		
	Grade 3	Severe or medically significant but not immediately life-threatening; hospitalization or prolongation of hospitalization indicated; disabling; limiting self-care ADL.		
	Grade 4	Life threatening consequences; urgent intervention indicated.		
	Grade 5	Death related to AE		
Seriousness	
A serious adverse event is any adverse event occurring at any dose or during any use of Merck product that:
 
†Results in death; or
 
†Is life threatening; or places the subject, in the view of the investigator, at immediate risk of death from the event as it occurred (Note: This does not include an adverse event that, had it occurred in a more severe form, might have caused death.); or
 
†Results in a persistent or significant disability/incapacity (substantial disruption of one's ability to conduct normal life functions); or
 
†Results in or prolongs an existing inpatient hospitalization (hospitalization is defined as an inpatient admission, regardless of length of stay, even if the hospitalization is a precautionary measure for continued observation. (Note: Hospitalization [including hospitalization for an elective procedure] for a preexisting condition which has not worsened does not constitute a serious adverse event.); or
 
†Is a congenital anomaly/birth defect (in offspring of subject taking the product regardless of time to diagnosis); or
 
Is a new cancer; (that is not a condition of the study) or
 
Is an overdose (whether accidental or intentional). Any adverse event associated with an overdose is considered a serious adverse event. An overdose that is not associated with an adverse event is considered a non-serious event of clinical interest and must be reported within 24 hours.
 
Other important medical events that may not result in death, not be life threatening, or not require hospitalization may be considered a serious adverse event when, based upon appropriate medical judgment, the event may jeopardize the subject and may require medical or surgical intervention to prevent one of the outcomes listed previously (designated above by a †).
			
Duration	Record the start and stop dates of the adverse event. If less than 1 day, indicate the appropriate length of time and units			
Action taken	Did the adverse event cause the Merck product to be discontinued?			
Relationship to test drug	
Did the Merck product cause the adverse event? The determination of the likelihood that the Merck product caused the adverse event will be provided by an investigator who is a qualified physician. The investigator's signed/dated initials on the source document or worksheet that supports the causality noted on the AE form, ensures that a medically qualified assessment of causality was done. This initialed document must be retained for the required regulatory time frame. The criteria below are intended as reference guidelines to assist the investigator in assessing the likelihood of a relationship between the test drug and the adverse event based upon the available information.
 
The following components are to be used to assess the relationship between the Merck product and the AE; the greater the correlation with the components and their respective elements (in number and/or intensity), the more likely the Merck product caused the adverse event (AE):
 
 
 Exposure	Is there evidence that the subject was actually exposed to the Merck product such as: reliable history, acceptable compliance assessment (pill count, diary, etc.), expected pharmacologic effect, or measurement of drug/metabolite in bodily specimen?	
 
		Exposure	Is there evidence that the subject was actually exposed to the Merck product such as: reliable history, acceptable compliance assessment (pill count, diary, etc.), expected pharmacologic effect, or measurement of drug/metabolite in bodily specimen?
Exposure	Is there evidence that the subject was actually exposed to the Merck product such as: reliable history, acceptable compliance assessment (pill count, diary, etc.), expected pharmacologic effect, or measurement of drug/metabolite in bodily specimen?			

	Time Course	Did the AE follow in a reasonable temporal sequence from administration of the Merck product? Is the time of onset of the AE compatible with a drug-induced effect (applies to trials with investigational medicinal product)?
	Likely Cause	Is the AE not reasonably explained by another etiology such as underlying disease, other drug(s)/vaccine(s), or other host or environmental factors
Relationship to Merck product (continued)	The following components are to be used to assess the relationship between the test drug and the AE: (continued)	
	Dechallenge	Was the Merck product discontinued or dose/exposure/frequency reduced? If yes, did the AE resolve or improve? If yes, this is a positive dechallenge. If no, this is a negative dechallenge. (Note: This criterion is not applicable if: (1) the AE resulted in death or permanent disability; (2) the AE resolved/improved despite continuation of the Merck product; or (3) the trial is a single-dose drug trial); or (4) Merck product(s) is/are only used one time.)
	Rechallenge	Was the subject re-exposed to the Merck product in this study? If yes, did the AE recur or worsen? If yes, this is a positive rechallenge. If no, this is a negative rechallenge. (Note: This criterion is not applicable if: (1) the initial AE resulted in death or permanent disability, or (2) the trial is a single-dose drug trial); or (3) Merck product(s) is/are used only one time). NOTE: IF A RECHALLENGE IS PLANNED FOR AN ADVERSE EVENT WHICH WAS SERIOUS AND WHICH MAY HAVE BEEN CAUSED BY THE MERCK PRODUCT, OR IF REEXPOSURE TO THE MERCK PRODUCT POSES ADDITIONAL POTENTIAL SIGNIFICANT RISK TO THE SUBJECT, THEN THE RECHALLENGE MUST BE APPROVED IN ADVANCE BY THE U.S. CLINICAL MONITOR AS PER DOSE MODIFICATION GUIDELINES IN THE PROTOCOL.
	Consistency with Trial Treatment Profile	Is the clinical/pathological presentation of the AE consistent with previous knowledge regarding the Merck product or drug class pharmacology or toxicology?
The assessment of relationship will be reported on the case report forms /worksheets by an investigator who is a qualified physician according to his/her best clinical judgment, including consideration of the above elements.		
Record one of the following		Use the following scale of criteria as guidance (not all criteria must be present to be indicative of a Merck product relationship).
Yes, there is a reasonable possibility of Merck product relationship.		There is evidence of exposure to the Merck product. The temporal sequence of the AE onset relative to the administration of the Merck product is reasonable. The AE is more likely explained by the Merck product than by another cause.
No, there is not a reasonable possibility Merck product relationship		Subject did not receive the Merck product OR temporal sequence of the AE onset relative to administration of the Merck product is not reasonable OR there is another obvious cause of the AE. (Also entered for a subject with overdose without an associated AE.)

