### 2.2 Secondary Objective(s) & Hypothesis(es)

(1) **Objective:** To determine the safety and tolerability of pembrolizumab (MK-3475), lenalidomide and dexamethasone following ASCT in subjects with high risk MM.

**Hypothesis:** Intravenous administration of pembrolizumab (MK-3475), lenalidomide and dexamethasone to subjects with high risk MM as consolidation therapy post ASCT is sufficiently well tolerated.

(2) **Objective:** To evaluate stringent complete response, complete response, and very good partial response rate (sCR + CR + VGPR rate) in subjects with high risk MM post-ASCT.

(3) **Objective:** To evaluate Overall Response Rate (ORR) in subjects with high risk MM post-ASCT.

(4) **Objective:** To evaluate Time to Progression (TTP) in subjects with high risk MM post-ASCT.

(5) **Objective:** To evaluate Duration of Response (DOR) in subjects with high risk MM post-ASCT.

(6) **Objective:** To evaluate Overall Survival (OS) in subjects with high risk MM post-ASCT.

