#### 4.2.1.3 Dose Modification Guidelines for Lenalidomide

Dose modification guidelines are based on the recommendation provided by the Myeloma expert panel review[58] of the efficacy and toxicity of lenalidomide plus dexamethasone, and the guidance provided in the product label for lenalidomide. Any toxicity associated with lenalidomide that prompts a dose reduction of lenalidomide is outlined in the Sections below.

Lenalidomide is administered once daily from Day 1 through Day 14 in each 21 day cycle. If a subject receiving 5 mg of lenalidomide experiences an AE related to lenalidomide and is in need of dose modification, the subject should discontinue lenalidomide and continue only pembrolizumab (MK-3475) and dexamethasone, as 5 mg is the lowest dose used in

Pembrolizumab (MK-3475), [name], HUMC

this trial. A maximum of three dose reductions of lenalidomide will be allowed in the order indicated in Table 6, where applicable. The duration of administration will remain the same.

A subject cannot be restarted on lenalidomide unless non-hematologic lenalidomide-related toxicities have returned to at least Grade 1 toxicity or baseline.

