7. After documented disease progression or the start of new antineoplastic therapy, each subject will be followed by telephone for overall survival until death, withdrawal consent or the end of the trial, whichever occurs first.
8. AEs and laboratory safety measurements will be graded per NCI CTCAE version 4.03. All AEs, whether gradable by CTCAE or not, will also be evaluated for seriousness. AEs will be evaluated every two weeks, on Days 1 and 15 of each 21-day cycle.
9. Record all AEs occurring within 30 days after the last dose of study drug. Report all SAEs (related and unrelated to trial treatment) and ECIs occurring up until 90 days after the last dose of trial treatment or the start of new anti-cancer treatment, whichever comes first. Afterwards, report only SAEs and ECIs that are related to trial treatment.
10. Directed PE performed to collect any new/clinically significant abnormalities (i.e. ECI/AE).
11. Vital signs to include temperature, pulse, respiratory rate, weight and blood pressure. Height will be measured at screening only.
12. Skeletal survey should include a chest (PA or AP; lateral), skull (lateral), upper extremities (shoulder to elbow), lower extremities (hip to knee; AP), pelvis (AP), cervical/thoracic/lumbar spine (AP and lateral). For suspected progression to bone disease bidimensional measurement of the target lytic lesions must be performed. MRI/CT/PET (MRI for subjects with bone disease and CT/PET for plasmacytomas) is required when clinically indicated for subjects with bony disease and should just include the bony lesions. Subjects with measurable plasmacytomas at baseline should have imaging performed every 12 weeks.
13. Disease response assessment is based upon the multiple myeloma response criteria (See Appendix 5 ). Myeloma lab assessments should be performed every 3 weeks, that is, on Day 1 of every 21-day treatment cycle. Disease assessments should occur at Day 1 of each 21-day treatment cycle (+/- 7 days) throughout the course of the trial.

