### 7.1.8.2 Statistical Methods for Safety Analyses

Safety and tolerability will be assessed by clinical review of all relevant parameters including adverse experiences (AEs), ECOG, laboratory tests, vital signs, and ECG measurements.

Summary statistics (median and range) for time to onset of first drug-related toxicity in each dose level will be provided. Adverse experiences will be summarized as counts, frequencies and grade by NCI CTCAE version 4.03. Laboratory values will be graded by NCI CTCAE version 4.03. The percentage of subjects with laboratory abnormalities by grades will be tabulated. The change of grades during the study will be summarized by a lab shift table. In this analysis, the percentage of subjects who improve or worsen from baseline for each laboratory test will be summarized. A clinically meaningful worsening in CTCAE grade was defined as a shift from less than Grade 3 at baseline to Grade 3 or above, or a shift from Grade 0 to Grade 2. Summary statistics for baseline, on-treatment, and change from baseline values of continuous measures such as changes from baseline in ECOG, laboratory, vital signs, and ECG parameters will be provided by dose-level in table format. Immune-related AEs (irAEs) that are designated as events of special interest will be summarized separately from other AEs.

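### Table 11 records AE causality and action taken for the Merck product only, so a three-drug safety objective needs per-drug fields and a definition of drug-related

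*Combined protocol and SAP*

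**What the plan says.** The safety objective in section 2.2 is about the regimen: "To determine the safety and tolerability of pembrolizumab (MK-3475), lenalidomide and dexamethasone following ASCT in subjects with high risk MM".

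Causality is assessed with Table 11 in section 6.2.4. Its relationship question is "Did the Merck product cause the adverse event", answered by a single Yes or No. Its action-taken item is "Did the adverse event cause the Merck product to be discontinued". No is the answer when, among other conditions, "there is another obvious cause of the AE", and the likely-cause component lists other drugs among the alternative explanations.

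Other sections are broader. Section 3.2.3.2 says that attribution to drug will be recorded, without naming a drug. Section 6.1.2.1 wants causality and the action taken on trial treatment. The dose-modification rules need judgements about single drugs; section 4.2.1.3 states "A subject cannot be restarted on lenalidomide unless non-hematologic lenalidomide-related toxicities have returned" to a set grade or baseline, and sections 4.2.1.3.1 and 4.2.1.4 contain similar conditions for lenalidomide and dexamethasone.

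The analysis plan uses drug-related without defining it: in the FAS (7.1.7.1), in the AE evaluable population (7.1.7.2), and in the summary of "time to onset of first drug-related toxicity" (7.1.8.2).

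For SAEs after the 90-day window, section 6.2.3.1 requires those "considered by an investigator who is a qualified physician to be related to Merck product", while flow-chart footnote 9 says to "report only SAEs and ECIs that are related to trial treatment".

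**The concern.** The trial sets out to describe the tolerability of three drugs given together, but the instrument asks about one of them. An investigator who follows Table 11 as written has nowhere to record that lenalidomide or dexamethasone caused an event, or that either was reduced or stopped because of it. Section 3.2.1.4 itself lists cytopenias, rash, infection and venous thromboembolism among the most common Grade 3-4 events with lenalidomide plus dexamethasone, so such attributions are to be expected.

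Two things are at stake. A drug-related summary could be read as describing the regimen when it describes pembrolizumab alone. And because drug-related also decides membership of two analysis sets, the coding could determine who is counted as well as how an event is labelled.

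**Working it through.** The plan states no figure that depends on causality coding, so there is none to reproduce. The check is a comparison of the text, followed by an illustration on assumed counts.

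**1. Which drugs does Table 11 cover?** Section 6.2 limits Merck product to what Merck makes, licenses, provides or distributes. Section 4.7.2 calls lenalidomide the Celgene product and has unused drug returned to Celgene, so it falls outside. No supplier is named for dexamethasone. It falls outside unless Merck provides it.

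**2. How is a lenalidomide-caused event coded?** Yes describes an event better explained by the Merck product than by another cause. Another drug counts as an alternative explanation, and another obvious cause leads to No. A toxicity clearly due to lenalidomide is therefore coded No. Where attribution among drugs given together is unclear, the investigator's judgement decides and either answer is possible.

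**3. Do the broader sections supply the missing field?** Section 6.1.2.1 refers to section 6.2 for the detail of assessing and recording AEs, which leads back to Table 11. Section 3.2.3.2 names neither a drug nor a field. Sections 4.2.1.3, 4.2.1.3.1 and 4.2.1.4 require drug-specific judgements but describe no AE field for them. Together they show that wider attribution is intended, without providing a place to record it. The action-taken item also covers discontinuation only, although the plan allows up to three lenalidomide and two dexamethasone reductions.

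**4. Where does drug-related enter the analysis?**
- *Time to first drug-related toxicity (7.1.8.2).* If taken from Table 11, it is the time to first pembrolizumab-related toxicity.
- *AE evaluable population (7.1.7.2).* A subject who does not complete cycle 1 is included only if a drug-related AE caused discontinuation from the trial. One who leaves the trial in cycle 1 for a lenalidomide toxicity coded No is excluded. One who stops lenalidomide but completes the cycle on the other drugs is not.
- *FAS (7.1.7.1).* A treated subject with no post-baseline disease assessment enters only through discontinuation for progression or a drug-related AE. Exclusion is possible but less likely, since section 6.1.4.1 asks for final-visit procedures at discontinuation.

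**5. Illustration of the AE evaluable effect.** Assume all 43 planned patients are treated, *m* have the AE of interest, and *k* of those *m* leave in cycle 1 for a lenalidomide or dexamethasone toxicity coded No. The rate changes from *m*/43 to (*m* − *k*)/(43 − *k*).
- *m* = 10: 10/43 = 23.3%; with *k* = 1, 9/42 = 21.4%; with *k* = 4, 6/39 = 15.4%.
- *m* = 20: 20/43 = 46.5%; with *k* = 1, 19/42 = 45.2%; with *k* = 4, 16/39 = 41.0%.

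The values of *m* and *k* are assumptions; the documents give no toxicity rates for this regimen in this setting.

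**6. Late SAEs.** Take a new cancer, which section 6.2.3.1 lists as serious, arising after the 90-day window and attributed by the investigator to lenalidomide. Under 6.2.3.1 it need not be reported, because it is not related to Merck product. Under footnote 9 it must be, because lenalidomide is trial treatment. The Trial Summary gives a third rule: SAEs are collected until progression, with no condition on relationship.

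**The case against.** A reader might infer that causality is recorded nowhere for the other two drugs, that the drug-related results will be wrong, and that the attribution is lost for good. The documents do not support that. Sections 3.2.3.2 and 6.1.2.1 call for wider recording, the AE form itself is not in the documents, and investigators must judge lenalidomide- and dexamethasone-relatedness to apply the dose rules. Source notes, AE dates and drug accountability data could allow partial reconstruction. Nothing ties drug-related to the Table 11 field, and an analyst could read it as related to any study drug. Table 11 also presents its scale as guidance, subject to clinical judgement.

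Nor should the effect be expressed as a number of patients missing from a drug-related rate. No such rate table is planned: AE counts, frequencies and grades are not limited to related events. Lenalidomide's 14 × 4 = 56 dosing days out of 21 × 4 = 84 describe exposure, not attribution.

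It would be equally wrong to infer a flaw in safety monitoring. Both stopping rules in section 7.1.2 apply regardless of relationship. Lenalidomide interruptions under Tables 4 and 5 start from platelet and neutrophil thresholds, which laboratory data can verify.

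All of this stands and limits the point. It does not remove the mismatch between Table 11 and the three-drug objective, the undefined term that governs two analysis sets and one summary, or the late-SAE conflict.

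**Conclusion.** The point holds as an inconsistency with a conditional consequence. Applied as written, Table 11 yields a pembrolizumab attribution for a regimen-level safety objective, and does not capture toxicity clearly due to lenalidomide as related. The same applies to dexamethasone on the assumption that Merck does not supply it. If drug-related is drawn from that field, the onset summary describes one drug, and some patients who leave in cycle 1 can be excluded from the AE evaluable population and possibly the FAS.

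The size cannot be determined from the documents; the illustrated shifts run from 1.3 percentage points (46.5% to 45.2%) to 7.9 (23.3% to 15.4%) and depend wholly on the assumed counts. The stopping rules, the all-cause AE tables in the ASaT population and PFS in the ITT population do not use causality. The PFS statement relies on section 7.1.7.1 and Table 13; Table 12 names the FAS for PFS.

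The late-SAE conflict is separate and needs no assumption about how the analysis is run. The change should be made, because it is cheap and attribution is more reliably collected prospectively than reconstructed.

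**What to change.** - In Table 11 and on the AE form, record relationship and action taken separately for pembrolizumab, lenalidomide and dexamethasone, with action taken covering reduction and interruption as well as discontinuation.
- In sections 7.1.7 and 7.1.8.2, define drug-related as related to at least one of the three trial drugs.
- Align Table 11 with sections 3.2.3.2 and 6.1.2.1.
- Reconcile the late-SAE wording of section 6.2.3.1 with flow-chart footnote 9 and the Trial Summary, so that one rule states which late SAEs are reportable.

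The cost is two further sets of AE fields, amendment wording and a little more data entry. The pembrolizumab attribution sent to Merck is unchanged, and no dose or clinical rule is affected.
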